7.1.2 Adverse Device Effect

An adverse device effect (ADE) is defined as any AE that is related to the use of the investigational medical device.

7.1.3 Device Deficiency, Malfunction, and User Error

Investigators are instructed to report all possible device deficiencies, malfunctions or user errors during the course of the trial. These incidents will be documented in the eCRF as follows:

- ♦ **Device Deficiency** (ISO 14155:2011): Inadequacy of a medical device with respect to its identity, quality, durability, reliability, safety, or performance
- ♦ **Device Malfunction**: Failure of a device to meet its performance specifications or otherwise perform as intended [21 CFR 803.3].
- ♦ **User Error**: Device-related error or mistake made by the person using the device.

7.1.4 Serious Adverse Events

A **serious adverse event** (SAE) is any adverse experience occurring at any dose that results in any of the following outcomes:

- ♦ Results in **death.**
- ♦ Is a **life-threatening** adverse experience. The term "life-threatening" in the definition of "serious" refers to an adverse event in which the subject was at risk of death at the time of the event. It does not refer to an adverse event which hypothetically might have caused death if it were more severe.
- ♦ Requires **inpatient hospitalization or prolongation of existing hospitalization**. Any adverse event leading to hospitalization or prolongation of hospitalization will be considered as Serious, UNLESS at least one of the following expectations is met:
 - **o** The admission results in a hospital stay of less than 24 hours; OR
 - **o** The admission is pre-planned (e.g., elective or scheduled surgery arranged prior to the start of the study); OR
 - **o** The admission is not associated with an adverse event (e.g., social hospitalization for purposes of respite care.

However it should be noted that invasive treatment during any hospitalization may fulfill the criteria of "medically important" and as such may be reportable as a serious adverse event dependent on clinical judgment. In addition, where local regulatory authorities specifically require a more stringent definition, the local regulation takes precedent.

- ♦ Results in **persistent or significant disability/incapacity**. The definition of disability is a substantial disruption of a person's ability to conduct normal life's functions.
- ♦ Is a **congenital anomaly/birth defect**.
- ♦ Is an **important medical event**. Important medical events that may not result death, be life-threatening, or require hospitalization may be considered a serious adverse experience when, based upon appropriate medical judgment, they may jeopardize the subject and may require medical or surgical

IRB# 1331496 Page 35 Version 6.0

intervention to prevent one of the outcomes listed in this definition. Examples of such medical events include allergic bronchospasm requiring intensive treatment in an emergency room or at home, blood disease or disorders, or convulsions that do not result in inpatient hospitalization, or the development of drug dependency or drug abuse. The development of a new cancer is always considered an important medical event.

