7.1.5 Serious Adverse Device Effect

A serious adverse device effect (SADE) is any ADE that has resulted in any of the consequences characteristic of an SAE.

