7.3.1 Reporting of Serious Adverse Events

Reporting of SAEs includes reporting of any SAE, any medical device deficiency that might have led to an SAE, and any new finding / update in relation to already reported events.

It is the responsibility of the Principal Investigator or designee to report all SAEs to Noxsano, Inc. (the study device manufacturer) within **2 business days** of discovery or notification of the event.

[figure not shown]
It is the responsibility of the Principal Investigator or designee to report all SAEs according to the IRB of record's policies and procedures.

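### The exceptions in 7.1.4 describe only the admission but also switch off the prolongation criterion, so an adverse event that prolongs a pre-planned or non-AE admission may not be classified or reported as an SAE

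*Combined protocol and SAP*

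**What the plan says.** In 7.1.4 of the protocol, one of the outcomes that makes an adverse event serious is "inpatient hospitalization or prolongation of existing hospitalization". The next sentence restricts it: "Any adverse event leading to hospitalization or prolongation of hospitalization will be considered as Serious, UNLESS at least one of the following" conditions is met. Three alternatives follow, joined by OR:

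- "The admission results in a hospital stay of less than 24 hours"
- "The admission is pre-planned (e.g., elective or scheduled surgery arranged prior to the start of the study"
- "The admission is not associated with an adverse event (e.g., social hospitalization for purposes of respite care"

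A note after the list says that invasive treatment during a hospital stay may count as medically important, subject to clinical judgment, and that a stricter definition required by local regulators prevails. Death, life-threatening events, disability, congenital anomaly and important medical events are separate criteria.

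Seriousness is used in four later places. Section 7.2 makes it a recorded characteristic of every AE. Section 7.1.5 defines a SADE as "any ADE that has resulted in any of the consequences characteristic of an SAE". Section 7.1.6 builds the UADE definition partly on serious AEs. Section 7.3.1 requires the investigator "to report all SAEs to Noxsano, Inc. (the study device manufacturer) within" 2 business days, and to report SAEs under the IRB's own procedures.

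**The concern.** The headline names two outcomes: being admitted because of an event, and being kept in longer because of one. The exceptions are sensible for the first, since an elective or social admission is not in itself a harm. They do not fit the second. An event that arises during an elective stay and extends it is the kind of case the prolongation limb exists for, and the reason for the admission says nothing about it. Because a single UNLESS clause governs both outcomes and any one exception is enough, the exceptions reach the second outcome as well.

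At stake are the seriousness field on the AE form and the timed report to the manufacturer, in a first-in-human device study. The situation is conceivable in Group 2. These subjects have diabetic or arterial limb ulcers, they may be in the study for up to 15 months (3.3), and nothing in 4.5 excludes a subject with an admission already arranged.

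**Working it through.** There is no planned figure to reproduce. The check is a clause-by-clause reading of 7.1.4, followed through the sections that depend on it.

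**Step 1: scope of the exceptions.** The UNLESS sentence names hospitalization and prolongation together. The subject of each of the three exceptions is the admission.

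**Step 2: apply the rule by type of existing admission**, for an AE whose only consequence is a longer stay.

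| Existing admission | Exception met | Serious under this criterion, read literally? |
|---|---|---|
| Pre-planned | second | No |
| For a non-AE reason, such as respite care | third | No |
| Unplanned, caused by an earlier AE, 24 hours or more | none | Yes |

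The second row leaves some room: a reader could say that an admission prolonged by an AE has become associated with one. The first row leaves none, because an admission arranged before the study remains pre-planned whatever happens during it. The under-24-hours exception matters little here, since it is met only if the whole stay, extension included, remains under 24 hours.

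**Step 3: two hypothetical records.** In record A, a subject enters hospital for surgery arranged before the study, a device-site infection develops, and the stay lengthens from 3 to 8 days (8 − 3 = 5 extra days). In record B, the same infection causes a new, unplanned 5-day admission. Both events cost 5 hospital days. Under this criterion B is serious and A is not.

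**Step 4: other routes to seriousness for record A.** Death, a life-threatening course or lasting disability would make it serious, but a prolongation-only event has none of these. The invasive-treatment note and the important-medical-event criterion are both worded with *may* and rest on judgment. Five days of non-invasive treatment need not trigger either. The local-regulation clause helps only where a stricter definition exists, and 7.1.4 names none. A mandatory criterion has become a discretionary one.

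**Step 5: downstream effect.**

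- 7.2: seriousness could be recorded as no.
- 7.3.1: neither the 2-business-day report to the manufacturer nor the IRB report for SAEs would be triggered.
- 7.1.5: this depends on the reading. A SADE is defined by consequences, and prolongation is a listed consequence. If the exceptions are taken to qualify only SAE status, the event is still a SADE; if they carry over, it is not.
- 7.1.6: the UADE definition also has a residual limb for other unanticipated serious device-related problems, which does not depend on the 7.1.4 exceptions.
- 7.3: every AE, serious or not, is still recorded.
- 9.0: no SAE, SADE or UADE count or proportion is specified.

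**The case against.** The strongest reply is that this is loose wording that a sensible investigator would not apply literally. The headline lists prolongation, the exceptions speak of the admission, and a reader can confine them to admissions. That reading is available, but the text does not require it. UNLESS is capitalised, one exception suffices, and the sentence expressly includes prolongation. Two investigators could classify record A differently and both cite 7.1.4.

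A second reply is that the event does not disappear. That is right. It is recorded with severity, relatedness and action taken (7.2), and 7.3 has adverse events reported immediately to the Principal Investigator. In the example, a device-site infection also ends study treatment whatever its seriousness (5.11). What can be lost is the SAE label and the SAE reports.

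A third reply is that exposure is limited, and this also has force. Criterion 5b in 4.4 requires an ABI taken after revascularization, and 5c covers ulcers judged unsuitable for it, so planned revascularization is mainly open through the diabetic route, 5a. Device application lasts at most 3 months. Follow-up stops early for non-healing wounds (5.11), so 15 months is a ceiling.

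Three stronger inferences are tempting and should not be drawn:

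- *The protocol contradicts itself.* It is an exception drafted too broadly and in tension with its headline; other criteria can still make the event serious.
- *The event drops out of SADE and UADE status and of the safety counts.* SADE loss is arguable, UADE loss is not automatic, and section 9.0 plans no such counts.
- *One to three Group 2 subjects are affected.* That figure comes from assuming that 10% to 30% of the 10 subjects have a planned admission (10 × 0.1 = 1; 10 × 0.3 = 3). It counts planned admissions, not misclassified events. Misclassification also needs an AE that prolongs the stay, no other criterion met, and a literal reading by the site. The documents give none of these rates.

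**Conclusion.** The point holds as a wording defect in a safety definition. Read literally, 7.1.4 removes an AE that prolongs a pre-planned admission, and on the natural reading one that prolongs a non-AE admission, from the hospitalization/prolongation criterion. The remaining routes most likely to catch a prolongation-only event are discretionary or depend on a local rule that may not exist. The consequence is possible under-classification of seriousness and loss of the SAE reports in 7.3.1.

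The size cannot be stated, because the documents give no frequency of pre-planned or social admissions or of prolonged stays. In a group of 10, one subject is 1/10 = 10 percentage points of any serious-event proportion that might be reported, but the plan specifies no such proportion. Sample size, error rates and the primary endpoint are untouched. The conclusion assumes that sites apply the UNLESS sentence as written and that no stricter local definition applies.

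**What to change.** Reconcile the exceptions with the prolongation limb by adding one sentence after the list in 7.1.4, for example: *These exceptions apply to the admission only; an adverse event that prolongs any hospitalization, including a pre-planned one, meets this criterion.* The three exceptions can otherwise stay as they are. The same sentence should appear in any instructions for completing the SAE form. It would help to say whether an extended stay that still totals under 24 hours counts, since the added sentence would bring it in. A cross-reference in 7.1.5 would settle whether the exceptions bear on SADE status.

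The cost is a short protocol amendment and possibly a few more SAE reports. No visit, procedure or analysis changes.

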7.1.5 Serious Adverse Device Effect

A serious adverse device effect (SADE) is any ADE that has resulted in any of the consequences characteristic of an SAE.

7.1.6 Unanticipated Adverse Device Effect

An unanticipated device effect (UADE) is defined in 21 CFR 812.3 as any serious AE on health or safety or any life-threatening problem or death caused by, or associated with, a device, if that effect, problem, or death was not previously identified in nature, severity or degree of incidence in the protocol, or any other unanticipated serious problem associated with a device that relates to the rights, safety, or welfare of a subject.

7.1.7 Unexpected

Any AE that is not consistent in specificity or severity with the current protocol, including all amendments, is considered unexpected.

7.2 Documentation

Adverse events will be documented on the appropriate eCRF. All AEs will be characterized by the following criteria:

- ♦ Seriousness
- ♦ Intensity or severity
- ♦ Relatedness to the device and procedure
- ♦ Outcome
- ♦ Treatment or action taken
- ♦ Determination to continue study participation

7.2.1 Intensity or Severity

[figure not shown]
Intensity or severity will be recorded as mild, moderate, or severe using the following definitions:

- ♦ **Mild:** Minor signs/symptoms; no specific medical intervention required; asymptomatic laboratory findings only; marginal clinical relevance Subject is aware of symptoms, but symptoms are easily tolerated.
- ♦ **Moderate:** Requiring minimal, local, or noninvasive intervention only. Symptoms interfere with normal daily activities.
- Severe: Significant symptoms requiring hospitalization or invasive intervention. Symptoms are incapacitating.

7.2.2 Relatedness

Relatedness to the device and procedure will be recorded as unrelated, possibly related, or related.

IRB# 1331496 Page 36 Version 6.0

7.2.3 Outcome

Outcome will be recorded as ongoing, resolved with sequelae, or resolved without sequelae (with the date resolved).

7.3 Reporting of Adverse Events

The Principal Investigator or designee is responsible for ensuring that all AEs (both serious and non-serious) observed by the clinical team or reported by the subject which occur after the subject has signed the informed consent are fully recorded in the subject's medical record. Source documentation must be available to support all adverse events.

A critical limb wound care podiatrist is on call 24/7/365. Subjects will be instructed to call the Critical Limb Care Center, and will be seen on an urgent basis as needed based on podiatrist recommendation. The adverse event will be immediately reported to the study Principal Investigator.

7.3.1 Reporting of Serious Adverse Events

Reporting of SAEs includes reporting of any SAE, any medical device deficiency that might have led to an SAE, and any new finding / update in relation to already reported events.

It is the responsibility of the Principal Investigator or designee to report all SAEs to Noxsano, Inc. (the study device manufacturer) within **2 business days** of discovery or notification of the event.

[figure not shown]
It is the responsibility of the Principal Investigator or designee to report all SAEs according to the IRB of record's policies and procedures.

7.3.2 Reporting of Unanticipated Adverse Device Effects

If a complication occurs that the Principal Investigator believes may be a potential UADE, the site should immediately contact the device supplier to determine reporting requirements.

It is the responsibility of the Principal Investigator or designee to report all UADEs according to the IRB of record's policies and procedures.

IRB# 1331496 Page 37 Version 6.0

8.0 STUDY ADMINISTRATION

8.1 Data Management

The Principal Investigator is required to prepare and maintain adequate and accurate case histories designed to record all observations and other data pertinent to the investigation.

The Research Electronic Data Capture (REDCap™) system will be utilized, as required by OHRI, for data collection for both accrual entry and trial data management. REDCap is an electronic data capture (EDC) system housed on secure servers maintained at OhioHealth. Access to data through REDCap is restricted by user accounts and assigned roles. Once logged into the REDCap system with a user ID and password, REDCap defines roles for each user which limits access to appropriate data. User information and passwords can be obtained by contacting the REDCap Administrator.

REDCap is designed with the capability for study setup, activation, tracking, reporting, data monitoring and review, and eligibility verification. This study will utilize electronic case report form (eCRF) completion in the REDCap database. A calendar of events and required eCRFs are available in REDCap.

8.2 Clinical and Safety Monitoring

Qualified monitors from CSSi LifeSciences representing the Funder (Noxsano, Inc.) will conduct on-site monitoring visits to ensure that all Investigators conduct the study in compliance with the protocol.

8.2.1 Background

The purpose of the Clinical Monitoring Plan for the Safety and Efficacy of the Noxsano Wound Care Bandage: A First-in Human Study, protocol number 1331496, is to ensure compliance with the Principles of International Conference on Harmonization - Good Clinical Practice (ICH-GCP).

[figure not shown]
8.2.2 Objectives

The main objectives of the Monitoring Plan are to:

- ♦ Ensure that the rights and well-being of human subjects are protected.
- ♦ Ensure that key reported trial data are accurate, complete, and verifiable from source documentation.
- ♦ Assure the study site is familiar with and follows the protocol.
- ♦ Assure the site is GCP compliant and compliant with applicable regulatory requirements.

"Safety and Efficacy of the Noxsano Wound Care Bandage: A First-in Human Study" is designed to determine the safety and effectiveness of the Noxsano device. The initial safety assessment will be conducted in healthy volunteers as part of an IRB-approved study. Once safety has been established, the efficacy and safety of the Noxsano device will be evaluated in subjects with an active wound as part of an IRB-approved study.

IRB# 1331496 Page 38 Version 6.0

8.2.3 Monitoring Plan

A site initiation visit will be conducted. At this visit, the regulatory binder will be reviewed to ensure that it contains all necessary documents. The monitor will ascertain that the Principal Investigator and study staff are knowledgeable about the protocol and proper use of the Noxsano device. The initial monitoring visit will be conducted within the first month of patient enrollment. Thereafter, interim visits will be conducted every 6-8 weeks. Additional visits will be scheduled to address unanticipated issues which require training, remediation, or site assistance.

During the monitoring visits, the Clinical Research Associate (CRA) will ensure that the trial is conducted and documented properly. The CRA will perform the monitoring tasks in accordance with the protocol specific requirements, ICH/GCP Guidelines, and other applicable regulatory requirements. The CRA will verify that written informed consent was obtained before each subject participated in the trial. The CRA will verify the accuracy and completeness of the Case Report Forms (CRFs) and source documents for every subject enrolled in the trial. During the course of monitoring visits, the CRA will ensure that the regulatory binder is complete and up to date.

8.3 Regulatory and Ethical Considerations

The study will be conducted in compliance with International Conference on Harmonization (ICH) guidelines and with all applicable federal (including 21 CFR parts 56 & 50), state, or local laws.

8.3.1 Role of the Principal Investigator

[figure not shown]
The Principal Investigator has the overall responsibility for the conduct of the study, including assurance that the study meets and is conducted within the regulatory requirements specified by each reviewing regulatory authority. The Principal Investigator is responsible for ensuring informed consent is obtained, proper quality monitoring is performed, and quality data is collected and reported.

Provision of written informed consent must be obtained prior to any study-related procedures. The Principal Investigator will ensure that the subject is given full and adequate oral and written information about the nature, purpose, possible risks, and possible benefits of the study as well as the subject's financial responsibility. Subjects must also be notified that they are free to discontinue/withdraw from the study at any time. The subject should be given the opportunity to ask questions and be allowed time to consider the information provided.

8.4 Record Retention

The Principal Investigator supervises the retention of all study documentation and will maintain study records and reports for a minimum of 3 years after the study is terminated or completed. Electronic files will be stored on password-protected computers, and paper files will be stored in a secure facility with limited access at the offices of OHRI.

IRB# 1331496 Page 39 Version 6.0

8.5 Audits and Inspections

Authorized representatives of the sponsor, OhioHealth Research Compliance (ORC), or a regulatory authority may visit the site to perform audits or inspections, including source data verification. The purpose of an audit or inspection is to systematically and independently examine all study-related activities and documents to determine whether these activities were conducted, and data were recorded, analysed, and accurately reported according to the protocol, Good Clinical Practice (GCP) guidelines, ICH guidelines, and any applicable regulatory requirements.

8.6 Subject Confidentiality

Subject confidentiality will be maintained throughout the clinical study to ensure that data can always be tracked to the source. For this purpose, a unique subject study number will be used that allows identification of all data reported for each subject.

Protected Health Information (PHI) will be treated and maintained in compliance with the Healthy Insurance Portability and Accountability Act of 1996 (HIPAA) Privacy Rule on the protection of individuals with regard to the processing of personal data.

8.7 Protocol Deviations

The Investigators and research staff will not deviate from the protocol without prior written approval of the Institutional Review Board except in medical emergencies.

It is the responsibility of the Principal Investigator or designee to report all protocol deviations according to the IRB of record's policies and procedures.

IRB# 1331496 Page 40 Version 6.0

9.0 STATISTICAL CONSIDERATIONS

Primary Objective.

Group 1 (Safety): Healthy Volunteers. The initial phase of the study is designed to determine the safety of the study device in normal healthy volunteers without wounds. If there are no issues with tolerance, side effects, and/or adverse reactions in normal healthy volunteers, the second phase of the study will proceed with active wound care subjects.

Group 2 (Efficacy): Wound Care Subjects. The second phase of the study is designed to determine the effectiveness of the study device in wound healing in subjects with active wounds (see Primary Endpoint below), and to determine if the study device is equivalent to standard and established techniques (standard techniques demonstrate 50% wound healing at 2 months).

Primary Endpoint.

The primary endpoint for this study is wound healing (Group 2), as defined by the percent change in wound surface area (surface area is calculated in cm²) from baseline through the active treatment period. Wound care subjects will have the study device applied (and re-applied weekly) until the wound is judged to be healed by the wound care practitioner, for up to 3 months total duration. If after 2 consecutive months of treatment with the study device the wound does not exhibit at least 50% improvement in surface area (cm²), the subject will be returned to standard and established techniques consistent with the wound etiology. We will also determine if the study device is equivalent to standard and established techniques (standard techniques demonstrate 50% wound healing at 2 months).

Statistical Analysis Plan.

Descriptive statistics will comprise the bulk of the statistical analysis. Continuous variables will be reported as means and standard deviations, along with median and minimum/maximum values and compared between baseline and follow-up times using paired t-tests and/ or repeated measures ANOVA. Dichotomous and categorical variables will be reported as frequencies with percentages and compared between follow-up times using Chi-square tests or Kruskal Wallis tests. Imputation techniques will be used to account for missing data. Statistical significance will be set at p<0.05 for all the tests.

IRB# 1331496 Page 41 Version 6.0

